## 7 STATISTICAL CONSIDERATIONS

---

### 7.1.1 Sample size

The primary objective in the present study is to compare the UF volume obtained with the Carry Life® UF device, at the glucose dose determined by the UF volume obtained during the in-clinic phase of the study, and the UF volume obtained by a standard 2.27% glucose dwell of the same duration when performed by the patient at home. Carry Life® UF is intended as an intermittent treatment in order to provide an additional removal of fluid in patients whose UF need is not met by their standard PD regimen. A UF volume  $\geq$  250 ml greater with the Carry Life® UF treatment than with the 2.27% glucose CAPD dwell is considered a clinically relevant UF volume. Assuming three 5-hour treatments with Carry Life® UF per week this corresponds to an increase in fluid removal of 750 ml/week.

The sample size is calculated using the UF volume data from a previous pilot study (Tmed-007) on eight subjects, with the aim to demonstrate a superiority margin,  $\delta$ , of 250 ml. For each subject the  $\delta$  UF volume between the control 2.27% CAPD dwell and the Carry Life® UF treatment (paired comparison) at either the 11 g/h or the 14 g/h glucose dose provided input to the sample size calculation. The glucose dose providing input was selected following the dose determination scheme described for the current study (refer to page 47). The difference between the Carry Life® UF and the control 2.27% CAPD dwell had a mean value of 574 ml and a standard deviation of 236 ml.

The sample size is estimated by

$$n = \frac{(z_\alpha + z_\beta)^2 \sigma_m^2}{2(\epsilon - \delta)^2}$$

where

$\epsilon$  = test - control

$\delta$  = superiority margin

$\sigma_m$  = standard deviation of the paired differences

Set

$\text{Alpha} = 0.025, Z_{\text{alpha}} = 1.96$

$\text{Power} = 0.80, Z_{\beta} = 0.842$

$\sigma_m = 236$

$\epsilon = 574$

$\delta = 250$

Assuming a standard deviation of 236 ml, an expected difference of 574 ml and a superiority margin of 250 ml requires a sample size of 3 to obtain 80% power for the superiority test ( $\alpha = 0.025$ ) using a one sample superiority (one-sided) t-test sample size calculation.

We also consider a more extreme case where we assume a standard deviation of 1.4 times the previous standard deviation, or 330 ml. Further, we lower our assumed mean difference to 400 ml (about 0.7s below the previous observed value). With these assumptions (standard deviation of 330

ml, an expected difference of 400 ml, and a superiority margin of 250 ml) we require a sample size of 19 to obtain 80% power for the superiority test ( $\alpha = 0.025$ ).

The study size of 25 was selected based on the conservative sample size with additional subjects to account for possible dropouts.

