-------------	---

	
A flow diagram of the study design is shown below (Figure 1). Refer to Table 1 for the schedule of activities at each visit.
 
Figure 1. Study flow chart
  <pre> graph LR     A[Screen. & Consent *] --> B[1 PET + 2 CLUF]     B --> C[Randomization]     C --> D[Grp. A]     C --> E[Grp. B]     C --> F[Grp. C]     C --> G[Grp. D]     D --> H[Control]     D --> I[T]     D --> J[CLUF 11 g/h]     E --> K[Control]     E --> L[T]     E --> M[CLUF 15 g/h]     F --> N[T]     F --> O[CLUF 11 g/h]     F --> P[Control]     G --> Q[T]     G --> R[CLUF 15 g/h]     G --> S[Control]   </pre> 
Abbreviations: CLUF = Carry Life® UF; Grp. = Group; PET = peritoneal equilibration test; Screen. = Screening; T = Transition to home phase with device training.    * A run-in period of at least two weeks may be performed in order to make an approved adjustment the PD prescription so that it can meet the study inclusion criteria

STUDY FOLLOW UP	The subject will be followed up for one (1) week for new or continuing AEs after the end-of-study visit. The follow-up will be in the form of a phone call or a physical meeting as required.
NUMBER OF SUBJECTS	Approximately 25 patients will be enrolled with a goal of 19 completing the study per protocol.
STUDY POPULATION	Adult subjects with end-stage kidney disease (ESKD) treated with CAPD.

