### 7.1.6 Statistical analysis of primary endpoint

The primary endpoint uses the UF measured per protocol at each efficacy evaluation treatment during the home treatment phase. Each subject is expected to have two efficacy evaluations per treatment arm. Subjects with one or more per protocol efficacy evaluations in each arm will be included in the primary endpoint analysis. The analysis will be performed for both the ITT and the PP population. Excluded subjects will be tabulated with narratives as to why they are missed efficacy evaluations.

For each subject, we use the mean  $UF_{CL}$  and the mean  $UF_{CAPD}$  for analysis. The mean difference (i.e., a paired comparison) between the UF achieved with the Carry Life® UF treatment and the UF achieved with the control CAPD dwell ( $UF_{CL}(n) - UF_{CAPD}$ ) will be calculated ( $UF_{diff}(n)$ ) with a 95% CI. A superiority (one sided t-test) test will be used to demonstrate that the Carry Life UF treatment is superior to the control with superiority margin of 250 ml. A superiority margin greater than 0 ml but less than 250 ml supports that the Carry Life® UF treatment increases UF as compared to the control, but at a level that may not be clinically significant.

For the primary endpoint analysis, the four groups (Group A, 11 g/h starting with control; Group B, 15 g/h starting with control, Group C, 11 g/h starting with Carry Life UF; Group D, 15 g/h starting with Carry Life UF) in the randomization scheme will be pooled. Control data generated from all four groups will be part of the control group and Carry Life UF data for both doses from all four groups will be part of the Carry Life UF group. This results in two final groups for primary endpoint analysis; control and Carry Life UF. Based on 1) prior pilot study results showing no significant difference between the doses and 2) our dose determination procedure, which assigns the glucose dose to be used by each subject based on the UF result in the in-clinic phase of the study, we expect the two Carry Life UF glucose dose groups to behave as a single population and be poolable for the purposes of the primary endpoint of the study. However, as part of our descriptive analysis, we intend to summarize the difference in UF volume between study arms for each Carry Life UF glucose dose as well as for different fill volumes.

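### Under the scenario that sets the trial size (SD 330 ml, difference 400 ml), 19 completers give about 47% power, not 80%, because the sample-size formula divides by 2 and its result is then used as the trial total

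*Protocol*

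**What the plan says.** Section 7.1.1 gives n = (z_alpha + z_beta)^2 sigma_m^2 / [2(epsilon - delta)^2]. It defines sigma_m as the "standard deviation of the paired differences" and describes the method as "using a one sample superiority (one-sided) t-test sample size calculation".

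Two cases are worked:

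- **Pilot values** (difference 574 ml, SD 236 ml): the plan "requires a sample size of 3 to obtain 80% power for the superiority test".
- **Conservative values** (difference 400 ml, SD 330 ml): "we require a sample size of 19 to obtain 80% power for the superiority test".

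The same section says that the study size of 25 rests on the conservative case plus an allowance for dropouts. The synopsis repeats both calculations and sets the target: "Approximately 25 patients will be enrolled with a goal of 19 completing the study per protocol". Section 6.3.1 gives the same target.

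The primary analysis in section 7.1.6 takes each subject's mean in each arm, forms one paired difference per subject and pools all four randomised groups: "A superiority (one sided t-test) test will be used to demonstrate that the Carry Life UF treatment is superior to the control with superiority margin" (set at 250 ml). The rejection rule in section 5.2, however, has a standard error of sigma_m/sqrt(2n) and 2n-2 degrees of freedom.

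**The concern.** Three statements cannot all stand: the formula with the 2, the label of a one-sample test on paired differences, and the use of n as the trial total. For a one-sample test with SD sigma_m of the differences, the variance of the mean difference is sigma_m^2/n, so the formula should have no 2. A formula with the 2, combined with the sqrt(2n) and 2n-2 of section 5.2, fits a two-sequence crossover with n subjects in each sequence and 2n in all. Section 7.1.5 does randomise 1:1 to two sequences. Read that way, 19 is half the required number.

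The stated power is what tells a reader how to interpret a non-significant result. The protocol implies that, if the true gain were 400 ml, the trial would have four chances in five of showing that it exceeds 250 ml. If the real chance is nearer one in two, a failed primary test could be misread as evidence against a clinically relevant gain.

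**Working it through.** **Inputs, all from section 7.1.1.** One-sided alpha 0.025 (z = 1.96); power 0.80 (z = 0.842); margin 250 ml. Conservative case: difference 400 ml, so 150 ml above the margin, SD 330 ml. Pilot case: difference 574 ml, so 324 ml above the margin, SD 236 ml.

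**Step 1: reproduce the protocol's figures.** (1.96 + 0.842)^2 = 7.851.

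| Case | With the divisor 2 | Without it |
|---|---|---|
| Conservative | 7.851 × 330^2 / (2 × 150^2) = 19.0, giving 19 | 38.0, giving 38 |
| Pilot | 7.851 × 236^2 / (2 × 324^2) = 2.08, giving 3 | 4.17, giving 5 |

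Both stated sizes come out only with the 2.

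**Step 2: power of the planned test.** This is a one-sample, one-sided t-test on n paired differences, with noncentrality (difference - 250)/SD × sqrt(n) and n-1 degrees of freedom. For 19 subjects in the conservative case, the noncentrality is 150/330 × sqrt(19) = 1.98 and the critical value on 18 degrees of freedom is 2.10. The noncentrality lies below the critical value, so power is under one half.

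| Case | Analysed in total | Exact power |
|---|---|---|
| Conservative | 19 | 46.6% |
| Conservative | 25 | 58.8% |
| Conservative | 38 | 77.9% |
| Conservative | 40 | 80.0% |
| Pilot | 3 | 27.9% |
| Pilot | 7 | 85.5% |
| Pilot | 19 | >99% |

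The normal approximation gives 50.9% at 19, so the shortfall comes mainly from the divisor and only slightly from the use of z in place of t. In the pilot case the approximation matters more: six subjects give 76.6%, so seven are needed. Analysed as a two-sequence design with 38 subjects and 36 degrees of freedom, the conservative case has 77.8% power, close to the intended 80%. This supports reading 19 as a per-sequence number.

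**Step 3: what 19 analysed subjects do support.** With SD 330 ml, 80% power needs a true difference of about 474 ml. With a difference of 400 ml, it needs an SD of no more than about 221 ml, which is below the pilot's own 236 ml.

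**Step 4: other readings that might rescue 80% at 19.**

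- One-sided alpha of 0.05 in place of 0.025: 60.3%.
- The 2 taken as the gain from averaging two evaluations per arm, with all of the variance behind the 330 ml arising within subjects: effective SD 330/sqrt(2) = 233 ml, power 75.5%. If none of it arises within subjects, power stays at 46.6%.

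Neither reaches 80%.

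**The case against.** The strongest reply is that the 47% belongs to a deliberately harsh scenario that worsens the mean and the SD together. With 19 analysed, changing only one input gives 74.5% (difference 400 ml, SD 236 ml) or 98.1% (difference 574 ml, SD 330 ml), and the pilot values give more than 99%. This is correct, and any statement of the 47% must carry its condition. But the protocol attaches its own 80% to exactly this scenario and says the trial size was chosen from it.

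Second, section 6.4.3 says that two treatments per arm are averaged to deal with variability. If the pilot SD came from single treatments, the SD relevant here would be below 330 ml. Power at 19 would then lie between 46.6% and 75.5%, and at 25 analysed the upper end would be 86.9%. More than 19 may be analysed, since Table 11 needs only one per-protocol evaluation per arm for the ITT analysis and withdrawn subjects may be replaced. The range is fair. But section 7.1.1 does not say that the 2 stands for averaging, that reading does not fit the 2n-2 degrees of freedom in section 5.2, and the 80% is claimed for 19.

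Third, no section defines n as a number per sequence. This is an inference from section 5.2, though a well-supported one. The finding does not depend on it: the formula does not match the named one-sample test on either reading.

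Finally, the pilot figure of 3 determines nothing in the trial, and the type I error is not affected by this point.

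**Conclusion.** The point holds. Under the assumptions to which the protocol attaches 80% power, a total of 19 analysed subjects gives 46.6%, a shortfall of about 33 percentage points, and 25 gives 58.8%. Reaching 80% takes 40. The calculation assumes that 330 ml is the SD of the per-subject paired differences actually analysed, as section 7.1.1 defines it. If it is instead a single-treatment SD, the figure at 19 is between 46.6% and 75.5%, still short of 80%.

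The trial is well powered if the pilot effect and SD carry over. What is wrong is the claim of 80% protection against a smaller effect with greater variability, and that claim is the stated basis for the enrolment target. It should be corrected before the result is interpreted.

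**What to change.** In section 7.1.1, either remove the 2 from the formula or state that n is per sequence and the total is 2n. Use the t distribution and restate the results: the conservative scenario needs 40 analysed subjects; 19 give about 47% power and 25 about 59%; the pilot scenario needs 7, not 3. Make the same correction in the synopsis. Align the rejection rule in section 5.2 in the same edit, since its sqrt(2n) and 2n-2 would otherwise contradict the corrected formula, and check the repeated target in section 6.3.1. If the averaging of two evaluations is meant to reduce the SD, say so and state the within-subject share assumed.

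The planned size can stay, provided it is openly justified by what 19 supports: the pilot values, or a true difference of about 475 ml at SD 330 ml. The cost is rewording and a less favourable stated power, with no extra patients. If the sponsor wants the 80% at 400 ml and SD 330 ml to be true, the trial must grow to 40 completers. At the protocol's own ratio of 19 completers to 25 enrolled, that is 40 × 25/19 = 52.6, or about 53 enrolled.

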#### 7.1.2 Intent-to-treat and per protocol population

The intent-to-treat (ITT) population is defined as all the included patients.

**Table 11. Definition of intention to treat and per protocol populations**

Endpoint Description	Intent-to treat (ITT) population	Per protocol (PP) population
Primary Endpoint		
Primary endpoint (UF volume)	Subjects with data from one or more per protocol efficacy evaluation treatments in each study arm.	Subjects with two per protocol efficacy evaluations treatments performed on the planned efficacy evaluation day and dwell of the day in each study arm.
Secondary Endpoints		
Safety endpoint (AEs and SAEs)	All the included subjects.	All subjects who complete four week's treatments in each study arm during the home treatment phase.
Peritoneal sodium removal and Glucose UF efficiency endpoints	Subjects with data from one or more per protocol efficacy evaluation treatments in each study arm.	Subjects with two per protocol efficacy evaluations treatments performed on the planned efficacy evaluation day and dwell of the day in each study arm.
Peak dialysate glucose concentration*	Subjects with in-clinic Carry Life UF per protocol treatments with one (1) to three (3) glucose dialysate results between T1h and T5h per glucose dose.	Subjects with in-clinic Carry Life UF treatments dialysate glucose samples from at least four (4) time points between T1h to T5h.

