CRITERIA FOR EVALUATION / STATISTICAL METHODS	
Primary endpoint
 

• The UF volume of the control CAPD dwell and the Carry Life® UF treatment will be measured per protocol at each efficacy evaluation treatment (two days per treatment arm) during the home treatment phase.

• Each subject is expected to have two efficacy evaluations per treatment arm. Subjects with one or more evaluations in each arm will be included in the primary endpoint analysis. Both the PP and ITT populations will be analyzed. Excluded subjects will be tabulated with narratives as to why they missed efficacy evaluations.

• A UF volume during the Carry Life® UF treatment exceeding with <math>\geq 250</math> ml the UF volume obtained with the 2.27% glucose CAPD dwell is considered clinically relevant.

 
Secondary endpoints
 

• AE and SAE rates: Based on all safety data gathered during the home treatment phase of the study for the Intent-To-Treat (ITT) dataset, AE and SAE occurrences will be collected, summarized, and presented.

• Peritoneal sodium removal:

◦ Based on data gathered from the efficacy evaluation treatments during the home treatment phase of the study, peritoneal sodium removal will be calculated and summarized.

◦ Each subject is expected to have two efficacy evaluations per treatment arm. Subjects with one or more evaluations in each arm will be included in the endpoint analysis. Excluded subjects will be tabulated with narratives as to why they missed efficacy evaluations.

◦ A statistically significant increase in sodium removal between the Carry Life UF treatment and the 2.27% glucose CAPD dwell will be determined by a t-test.

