#### 7.1.4 Per protocol treatments

Carry Life UF per protocol treatments are Carry Life UF treatments for which the Carry Life UF treatment with a treatment time of  $5 \pm 0.75$  hours and a total stop time during treatment of at most 30 min.

CAPD per protocol treatments are CAPD treatments with a total treatment time of  $5 \pm 0.75$  hours.

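### Table 11 limits the efficacy ITT set to per-protocol treatments, so a stop-time limit that only device treatments can fail filters both ITT and PP; its peak-glucose row makes the two sets disjoint

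*Protocol*

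**What the plan says.** **General definition.** Section 7.1.2 states: "The intent-to-treat (ITT) population is defined as all the included patients". Table 11, under the same heading, follows this only in its safety row.

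**Efficacy rows.** For UF volume, sodium removal and glucose UF efficiency, Table 11 gives the ITT set as "Subjects with data from one or more per protocol efficacy evaluation treatments in each study arm". The PP set needs two such treatments in each arm, on the planned day and dwell. Section 7.1.6 repeats the condition for the primary endpoint, "Subjects with one or more per protocol efficacy evaluations in each arm will be included in the primary endpoint analysis", and analyses both sets. The synopsis words the inclusion rule without it, "Subjects with one or more evaluations in each arm will be included in the primary endpoint analysis".

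**What per protocol means.** Under 7.1.4 a device treatment must last 5 ± 0.75 h and have "a total stop time during treatment of at most 30 min". For the control, "CAPD per protocol treatments are CAPD treatments with a total treatment time of" 5 ± 0.75 h, with no further condition.

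**Values averaged.** Sections 7.1.7.2 and 7.1.7.3 average only per-protocol evaluation treatments. For UF this is only implied: "The primary endpoint uses the UF measured per protocol at each efficacy evaluation treatment during the home treatment phase"; the synopsis likewise says UF "will be measured per protocol at each efficacy evaluation treatment".

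**Peak glucose.** Table 11 requires one to three dialysate results per glucose dose for ITT and at least four time points for PP. The per-protocol condition on the treatment stands in the ITT cell and not in the PP cell. The synopsis includes anyone with one or more sampling points. Section 7.1.7.4 specifies the mean and confidence interval for PP. The row carries an asterisk whose footnote is not in the text at hand.

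**The concern.** An ITT analysis beside a PP analysis normally shows whether the result depends on treatments having gone as planned. Here both efficacy sets require per-protocol treatments. They differ only in needing one treatment or two per arm, and in the planned day and dwell.

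The condition they share is not symmetric. A control dwell has no device to stop, so only device treatments can be removed for stop time. Section 2.6 attributes the device's sustained UF to continued glucose dosing. If a long stop lowers UF, removing those treatments raises the device mean and leaves the control mean alone.

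The primary objective (5.1.1) concerns a 5-hour device treatment at home, and 6.2.6 counts treatment time from the end of fill to the start of drain. An interrupted session that still runs its 5 hours can therefore fall within the question asked. At stake is whether the ITT result can be read as performance in home use, interruptions included.

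The peak-glucose row is a separate drafting error. Read literally, the most complete data belong to PP but not to ITT.

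**Working it through.** **1. Who is kept, by set (UF, sodium, glucose UF efficiency).**
- Device treatment of 5 ± 0.75 h with at most 30 min stopped: counts for ITT and for PP.
- Device treatment of 5 ± 0.75 h with more than 30 min stopped: counts for neither.
- Control dwell of 5 ± 0.75 h: counts for both.

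The second line has no control counterpart.

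**2. Size.** The protocol states no interruption rate and no UF loss per interruption, so there is no figure to reproduce. What follows rests on assumptions.

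Inputs from the protocol: pilot UF of 646 ml (11 g/h) and 739 ml (14 g/h) over 5 h (3.8); margin 250 ml, conservative SD 330 ml and n = 19 (7.1.1).

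Assumptions: a share p = 0.10 of device evaluation treatments is excluded (19 × 2 = 38 treatments, so about 4), each stopped for 30 to 60 min, with no UF while stopped.

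Loss per interrupted treatment, L:
- 646/5 = 129.2 ml/h; 0.5 h × 129.2 = 64.6 ml
- 739/5 = 147.8 ml/h; 1.0 h × 147.8 = 147.8 ml

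*Reading A, single treatments dropped from the subject's mean.* Bias = pL:
- 0.10 × 64.6 = 6.5 ml (2.6% of 250 ml)
- 0.10 × 147.8 = 14.8 ml (5.9% of 250 ml)

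*Reading B, only subjects with no per-protocol device treatment dropped, stops independent.* Among retained subjects the interrupted share is p(1 − p)/(1 − p²) = p/(1 + p). Bias = pL − pL/(1 + p) = p²L/(1 + p):
- 0.01 × 64.6/1.10 = 0.6 ml
- 0.01 × 147.8/1.10 = 1.3 ml

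*Effect on the test under reading A.* Take a true all-treatment difference of exactly 250 ml and a one-sample paired t-test. SE = 330/√19 = 75.7 ml. Noncentrality is 6.46/75.7 = 0.085 and 14.78/75.7 = 0.195. The one-sided error rises from 0.025 to 0.030 and 0.038.

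*Wider range.* With p from 0.05 to 0.20 and L from 64.6 to 300 ml, reading A gives 0.05 × 64.6 = 3.2 ml to 0.20 × 300 = 60 ml. Reading B gives 0.2 to 10 ml. A loss of 300 ml needs 300/147.8 = 2.0 h to 300/129.2 = 2.3 h without UF, so the upper end is remote.

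**3. Other endpoints.** Section 3.8 reports pilot sodium removal proportional to fluid removal, so sodium probably moves the same way. 86/646 = 0.133 and 92/739 = 0.124 mmol/ml, so reading A gives 6.46 × 0.133 = 0.9 mmol to 14.78 × 0.124 = 1.8 mmol. The pilot differences were 86 − 21 = 65 and 92 − 21 = 71 mmol. For glucose UF efficiency the direction is open: a stopped device also delivers less glucose, and pilot efficiency was higher at lower doses (17.0, 14.5 and 12.4 ml/g at 11, 14 and 20 g/h).

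**4. Peak-glucose row, membership by number of results from hour 1 to hour 5.**
- 0 results: neither set
- 1, 2 or 3: ITT only
- 4 or 5: PP only

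The intersection is empty, and a subject with all five results is outside ITT.

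**The case against.** **Table 11 may simply be endpoint-specific.** Section 7.1.11 speaks of ITT and PP as defined for each endpoint analysis, and a paired comparison cannot use every included patient, since some never reach the home phase. This stands, and makes part of the conflict one of labels. It explains requiring data in both arms. It does not explain the per-protocol qualifier.

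**A session with the device stopped for over 30 min may not be the treatment under study.** That is a fair question for PP to answer. It does not justify the same restriction in the set called ITT.

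**A reader might infer that no planned analysis keeps interrupted treatments.** The protocol does not support that. Weekly UF is an exploratory endpoint compared across arms (7.1.8), built from all dwells and device treatments in the home phase (Table 7), with no stated stop-time filter. It is coarser: it uses nominal glucose volumes and mixes in the dwells switched to 1.36% glucose. It cannot replace an estimate from the evaluation treatments, but interruptions are not hidden there. Section 7.1.12 also lists all data.

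**A reader might infer a material inflation of the primary result.** That is not supported either. Rates are assumed, and zero UF while stopped is probably too pessimistic: pilot dialysate glucose stayed at 1.6% to 2.2%, so some gradient would remain in a pause.

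**Which set decides, and which treatments enter each subject's mean UF,** may properly be left to a SAP that is not at hand. Neither is raised as a fault. The inclusion rule in 7.1.7, without the per-protocol condition, is a general statement that later subsections narrow. The pointer in 7.1.11 to the sample-size section is a stale cross-reference.

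**Conclusion.** The point holds as a fault in the set definitions. For UF volume, sodium removal and glucose UF efficiency, the protocol's ITT set departs from its own 7.1.2 and carries a device-only stop-time filter into both populations. Comparing ITT with PP therefore cannot show whether long interruptions at home reduce the benefit in the evaluation treatments.

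The direction favours the device for UF only if stops lower UF. The size cannot be derived from the protocol and is probably small: about 6 to 15 ml or about 1 ml, depending on whether single treatments or whole subjects are dropped. This assumes 10% of device treatments excluded and no UF during stops of 30 to 60 min. The case for change rests on the lost check and the low cost, not on a demonstrated bias.

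The peak-glucose row is wrong as written, against the synopsis, but has little consequence because 7.1.7.4 specifies the mean and interval for PP.

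**What to change.** **Efficacy rows of Table 11.** For UF, sodium removal and glucose UF efficiency, define the ITT row, or relabel it modified ITT, as randomised subjects with at least one weighed evaluation treatment of 5 ± 0.75 h in each arm, whatever the stop time. Apply the 30 min stop-time limit in the PP set only. Word 7.1.6, 7.1.7.2 and 7.1.7.3 to match, so that the per-protocol treatment condition governs the PP analysis alone.

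**Peak-glucose row.** Change the ITT requirement from one to three results to one or more. Move the per-protocol treatment condition from the ITT cell to the PP cell. Define both cells separately for each glucose dose received. The last step is needed because, under 6.2.2, subjects with UF of 1.0 L or more at 11 g/h do not receive the 15 g/h treatment. If the ITT cell alone asks for results per dose, such subjects could still meet PP and not ITT. With all three changes PP is a subset of ITT.

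**Editorial.** Correct the cross-reference in 7.1.11.

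**Cost.** Wording only. Bags are weighed and dialysate collected on every evaluation day (Table 1 footnotes), so no new data are needed. The ITT difference may come out slightly smaller and more variable. Treatments outside 4.25 to 5.75 h, including device treatments ended early, remain excluded, so the proposed set is still not free of selection; those treatments should be listed. Lifting the window as well is not proposed: 6.2.6 states that a control dwell beyond 5 h would give equal or lower UF, so over-long control dwells could favour the device.
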